3.2.2 Risk/benefit and ethical assessment

There is preclinical in-vitro and in-vivo data to suggest that some tumours may be responsive to treatment with AZD8330. Preliminary Phase I data with other MEK inhibitors suggests the potential for clinical responses or prolonged stable disease in some patients for whom there are no recognised therapies (LoRusso P et al 2005, Adjei A et al 2006). The current study will recruit a similar patient population (with advanced disease, refractory to standard therapies or for which no standard therapies exist) as was recruited into the other MEK Phase I studies.

In order to preserve the safety of participating patients, we are incorporating into the study design close monitoring of all safety parameters and PK analysis in order to guide the dose escalation decisions.

The emerging pharmacokinetic (PK) and pharmacodynamic (PD) assay data, inhibition of phosphorylated ERK (pERK) in PBMCs for 0.5 to 60mg AZD8330 have been analysed in a population PK/PD model. Following administration of 20mg AZD8330 OD to steady state the population median inhibition of pERK was predicted to be approximately 80% of the baseline value at the time corresponding to the C_{max} . However, by 4h post-dose the percentage inhibition of pERK declined to approximately 40% of the baseline value. It is hypothesised that twice daily (BD) dosing will provide the potential benefit of greater duration of inhibition of the MEK pathway during the dosing interval.

Emerging safety data for AZD8330 has established an MTD of 20mg once daily (section 1.1.3). Although 40mg OD was a non-tolerated dose, the adverse events that defined its non-tolerability were generally reversible by cessation of AZD8330 and taking approximately 2 weeks to return to baseline. In general, there is precedence for drug-dose scheduling to have a significant effect on tolerability and for this reason, along with the emergent PK/PD profile, the investigation of a BD dose is considered to be clinically important and to have an acceptable risk-benefit profile.

There is currently no clinical experience with AZD8330. However, based on the preclinical safety and toxicology studies with AZD8330 and the preclinical and clinical safety profile of other MEK inhibitors, a rigorous safety evaluation package has been put in place to minimise potential risk to patients and to discover potential toxicities in a timely manner. Details of specific safety monitoring requirements (in addition to those routinely included in a Phase I oncology study) are given below and in Section 4.5.1.2.

- Soft tissue mineralisation: weekly measurement of calcium and phosphate for 5 weeks (4 weeks on part B), then 4 weekly thereafter
- APTT prolongation: weekly APTT, PT and TT measurement for 5 weeks (4 weeks in part B), then 4 weekly thereafter
- Oedema and fluid accumulation: Cardiac function assessments at baseline and during the study. Weight to be measured at every vital sign assessment. Specific analyses of urine to be done in event of peripheral oedema or persistent proteinuria.
- Dyspnoea and hypoxia: Assessments of pulse oximetry at baseline and during the study.
- Visual function disturbance: ophthalmologic examination at baseline and during the study.

Further details regarding these assessments are provided in Sections 4.5.1.2 and 4.5.2 of this protocol.

Specific inclusion / exclusion criteria and restrictions are also included in this protocol to minimise potential adverse events, for example excluding patients with a medical history of diseases associated with disorder of calcium homeostasis. Patients are also advised to refrain

from unprotected prolonged sun exposure due to the potential for phototoxicity related to AZD8330.

No reproductive toxicology studies have been performed with AZD8330, although data from the one-month rat and dog studies indicates that AZD8330 produces adverse effects in the testes and/or ovaries in preclinical species. Therefore, AZD8330 should not be administered to pregnant or breast-feeding women and conception while on treatment must be avoided. Male patients with sexual partners who are pregnant or who could become pregnant (ie, women of child-bearing potential) should use acceptable methods of contraception (See Section 3.3.5) for 16 weeks after completing the study to avoid pregnancy and/or potential adverse effects on the developing embryo. Women of childbearing potential are advised not to rely solely on hormone contraception due the potential for loss of contraceptive function as a consequence of CYP450 induction by AZD8330.

Given the extensive safety monitoring included in this study, and inclusion of a full review of safety, tolerability and pharmacokinetic data prior to each dose escalation decision, AstraZeneca considers the overall risk for the patients who participate in this study to assess the safety and tolerability of AZD8330 is acceptable due to the lack of highly effective alternative treatments in this patient population.

3.3 Selection of study population

3.3.1 Study selection record

Investigator(s) must keep a record of patients who were considered for enrolment but were never enrolled eg, patient screening log. This information is necessary to establish that the patient population was selected without bias.

3.3.2 Inclusion criteria

For inclusion in the study patients must fulfil all of the following criteria:

1. Provision of informed consent.
2. Male or female, aged 18 years or older.
3. Cancer which is refractory to standard therapies, or for which no standard therapies exist.
4. Measurable Lesions that can be accurately measured in at least one dimension (longest diameter to be recorded) as ≥ 20 mm with conventional techniques or as ≥ 10 mm with spiral CT scan or non measurable lesions according to the RECIST Criteria.
5. Laboratory value as listed below: (SI Units).

- Calculated serum creatinine clearance ≥ 50 mL/min (using Cockcroft-Gault formula (see [Appendix E](#)) or by 24 hour urine collection).
- 6. LVEF as determined at baseline MUGA/echocardiography at or above the normal level.
- 7. WHO performance status 0-2 (those with performance status 2 must have been stable with no deterioration over the previous 2 weeks).
- 8. Evidence of post-menopausal* status or negative urine or serum pregnancy test for female pre menopausal patients.

* Post menopausal females are defined as follows: Natural menopause with menses >1 year ago; radiation induced oophorectomy with last menses >1 year ago; chemotherapy induced menopause with 1 year interval since last menses; serum FSH and LH and plasma oestradiol levels in the postmenopausal range for the institution; bilateral oophorectomy or hysterectomy.

3.3.3 Inclusion criteria for optional host genetic research

For inclusion in the optional genetic research, patients must fulfil the following criterion:

1. Provision of informed consent for host genetic sampling (blood sample) and analyses.

If a patient declines to participate in the genetic research (see [Appendix D](#)), there will be no penalty or loss of benefit to the patient. The patient will not be excluded from other aspects of the study described in this Clinical Study Protocol, so long as they consent to the main study.

3.3.4 Exclusion criteria

Any of the following is regarded as a criterion for exclusion from the study:

1. Laboratory values as listed below: (SI Units)
 - Absolute Neutrophil Count (ANC) $< 1.5 \times 10^9/L$ (1500 per mm^3)
 - Platelets $< 100 \times 10^9/L$ (100,000 per mm^3)
 - Haemoglobin (Hgb) < 9.0 g/dL
 - Serum bilirubin ≥ 1.5 x Upper Limit of Normal (ULN)
 - Aspartate aminotransferase (AST/SGOT) or alanine aminotransferase (ALT/SGPT) ≥ 2.5 x ULN

- Serum calcium (corrected for albumin¹) outside of normal limits
 - Phosphate outside of normal limits
 - Serum potassium or magnesium outside of normal limits
2. Any radiotherapy, biological or chemotherapy within 21 days prior to starting the study (not including palliative radiotherapy at focal sites) or who have not recovered from side effects of their treatment
 3. Participation in an investigational drug study within the 30 days prior to entry or who have not recovered from clinically significant side effects of an investigational study drug
 4. Brain metastases or spinal cord compression unless treated and stable off steroids and anticonvulsants (for at least 1 month)
 5. Female patients who are breast feeding, or patients of reproductive potential not employing an effective method of birth control
 6. Any evidence of severe or uncontrolled systemic disease (e.g., severe hepatic impairment, severe renal impairment uncontrolled diabetes, acute uncontrolled infection) or current unstable or uncompensated respiratory or cardiac conditions or peripheral vascular disease including diabetic vasculopathy
 7. Parathyroid disorder or history of malignancy associated hypercalcaemia
 8. Evidence of active infection or active bleeding diatheses
 9. Recent major surgery within 4 weeks prior to entry into the study (excluding the placement of vascular access) which would prevent administration of study treatment
 10. Patients with documented cases of human immunodeficiency virus (HIV) or hepatitis B or C
 11. Refractory nausea and vomiting, chronic gastrointestinal diseases (eg, inflammatory bowel disease), or significant bowel resection that would preclude adequate absorption
 12. Previous treatment with a MEK inhibitor
 13. QTc interval > 450ms

¹ Corrected calcium (mmol/l) = Total calcium (mmol/l) + 0.02 x [40 – Serum albumin (g/l)]

14. Involvement in the planning and conduct of the study (applies to both AstraZeneca staff or staff at the study site)
15. Previous enrolment or randomisation of treatment in the present study
16. Clinical judgement by the Investigator that the patient should not participate in the study

3.3.5 Restrictions

- Females of childbearing age are required to use reliable contraception throughout dosing and for 4 weeks post dosing.
- All males with partners of childbearing potential or whose partners are pregnant must use barrier contraception for the duration of dosing and for 16 weeks post dosing.
- Reliable methods of contraception should be used consistently and correctly and acceptable methods include barrier methods, implants, injectables, some IUDs, sexual abstinence or vasectomised partner. It is possible that AZD8330 interacts with oral contraception so any female using oral contraception must also use a barrier method of contraception. Hormonal contraception alone is not acceptable.
- No Grapefruit or grapefruit juice to be consumed.
- AZD8330 should be taken on an empty stomach (no food or drink other than water for 2 hours prior to dosing and 1 hour after dosing).
- Avoid excessive sun exposure and use adequate sunscreen protection if sun exposure is anticipated.
- Patients who are receiving concomitant medications that are substrates for CYP450s 3A4, 1A2 and 2C9 should be monitored for clinical signs of reduced efficacy of these agents (<http://medicine.iupui.edu/flockhart/table.htm>). In particular, patients who are on anticoagulant therapy (eg, warfarin) should have their anticoagulation tested more frequently when receiving AZD8330.

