No reproductive toxicology studies have been performed with AZD8330, although data from the one-month rat and dog studies indicates that AZD8330 produces adverse effects in the testes and/or ovaries in preclinical species. Therefore, AZD8330 should not be administered to pregnant or breast-feeding women and conception while on treatment must be avoided. Male patients with sexual partners who are pregnant or who could become pregnant (ie, women of child-bearing potential) should use acceptable methods of contraception (see Section 3.3.5) for 16 weeks after completing the study to avoid pregnancy and/or potential adverse effects on the developing embryo. Patients who are receiving concomitant medications that are substrates for CYP450s 3A4, 1A2 and 2C19 should be monitored for clinical signs of reduced efficacy of these agents. AZD8330 was seen to induce 3A4 and to a lesser extent CYP1A2 over the anticipated therapeutic concentration range in vitro hepatocytes studies, the results for CYP2C19 induction were inconclusive. In particular, women of childbearing potential are advised not to rely solely on hormone contraception due the potential for loss of contraceptive function as a consequence of CYP450 induction by AZD8330.

As AZD8330 is metabolised through the CYP2C9 and 2C19 pathways, it is particularly important that concomitant medications that are known inhibitors/inducers of these enzymes (<http://medicine.iupui.edu/flockhart/table.htm>) are recorded in order to aid the pharmacokinetic interpretation of AZD8330 data.

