7.6 Study timetable and end of study

Before a subject's enrolment in the study and any study-related procedures are undertaken the following should be fulfilled:

- Signed Clinical Study Protocol and other agreements between AstraZeneca and the Principal Investigator/Study Site.

- Approval of the study by the Ethics Committee
- Approval of the study, if applicable, by the regulatory authority.

The overall timetable for the study is summarised below:

Study period		Phase of development
Estimated date of first patient enrolled	April 2007	Phase I
Estimated date of last patient completed	August 2010*	

* End of study is defined as the point at which the last patient has received 6 months of treatment with AZD8330, or has withdrawn from the study (whichever is sooner).

In Part A of this study, patients may continue to receive AZD8330 until disease progression or as long as they continue to derive benefit from treatment. Therefore, the time at which the last patient stops treatment cannot be precisely predetermined. The study endpoint is defined as the point at which the last patient has received 6 months of treatment with AZD8330, or has withdrawn from the study (whichever is sooner). The study database will be locked at this point and the Clinical Study Report will be written. Serious adverse event reports for any patients still receiving treatment after the end of study will be entered on the AstraZeneca Global Patient Safety database. The study database will not be updated with this information nor an addendum to the Clinical Study Report be written.

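### Section 3.3.5 both accepts and bars an implant or injectable used alone as contraception, and the rule for men differs between sections

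*Protocol*

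**What the plan says.** **Women.** One bullet of Section 3.3.5 makes three statements. It gives a list: "acceptable methods include barrier methods, implants, injectables, some IUDs, sexual abstinence or vasectomised partner". It notes a possible interaction with oral contraception and requires that "any female using oral contraception must also use a barrier method of contraception". It closes with "Hormonal contraception alone is not acceptable". Section 3.2.1 is softer: "women of childbearing potential are advised not to rely solely on hormone contraception due the potential for loss of contraceptive function". Section 3.2.2 repeats that advice.

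**Men.** Section 3.3.5 says that men with pregnant partners, or partners of childbearing potential, "must use barrier contraception for the duration of dosing and for 16 weeks post dosing". Sections 3.2.1 and 3.2.2 say that such men should use acceptable methods, pointing to 3.3.5, "for 16 weeks after completing the study to avoid pregnancy".

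**Eligibility.** Exclusion 5 in Section 3.3.4 bars "patients of reproductive potential not employing an effective method of birth control". It does not define an effective method and does not refer to 3.3.5.

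**End of study.** Section 7.6 states: "The study endpoint is defined as the point at which the last patient has received 6 months of treatment with AZD8330", or has withdrawn if that is sooner. Sections 3.1.2 and 7.6 both provide for patients who are still on treatment after that point.

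**The concern.** Section 3.3.5 is the operative text: it is the only place that lists contraceptive methods, and sites will use it to counsel patients. If its sentences give different answers for the same woman, two sites following the protocol in good faith can act in opposite ways.

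The safety reason is the sponsor's own. Sections 3.2.1 and 3.2.2 report that no reproductive toxicology studies have been done, that the one-month animal studies showed adverse effects in testes and/or ovaries, and that CYP450 induction by AZD8330 might impair hormonal contraception. That reason is not confined to the oral route, but the added-barrier sentence is.

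For men, the operative section and the rationale sections use different words for what is required and for when the 16 weeks begin.

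**Working it through.** No sample size, power or event figure is involved, so the check is mainly a comparison of text, with simple date arithmetic for the male period.

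**Step 1. A woman whose only method is an implant or injectable.** Assumption: these methods are hormonal. That is their ordinary meaning, but the protocol does not state it.

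| Text | Answer for this woman |
|---|---|
| 3.3.5, list of methods | Acceptable, no condition attached |
| 3.3.5, added-barrier sentence | Silent; it names oral contraception only |
| 3.3.5, last sentence of the bullet | Not acceptable |
| 3.2.1 and 3.2.2 | Advised against, not barred |
| 3.3.4, exclusion 5 | Undetermined; effective method undefined, no reference to 3.3.5 |

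The texts give different answers, and no sentence says which prevails. A woman taking only an oral contraceptive gets a single answer from 3.3.5, because the added-barrier sentence and the last sentence agree. The conflict is therefore specific to the hormonal methods that appear on the list.

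**Step 2. The rule for men.**

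| Element | 3.3.5 | 3.2.1 and 3.2.2 |
|---|---|---|
| Force | Must | Should |
| Method | Barrier | Acceptable methods, by reference to 3.3.5 |
| Post-treatment length | 16 weeks | 16 weeks |
| Start of that period | End of dosing | Completion of the study |

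The length agrees: 16 × 7 = 112 days. The starting point does not, and completion can be read in at least two ways:

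- *Patient-level completion.* Section 4.5.1.2 describes study completion as following any scheduled follow-up, and Table 1 has a visit 30 days after the last dose. On that reading the 3.2.1/3.2.2 period ends 30 + 112 = 142 days after the last dose, against 112 days under 3.3.5. It ends later.
- *Study-level end under Section 7.6.* If a man is dosed for T days beyond that date, the 3.2.1/3.2.2 period ends 112 − T days after his last dose. It ends earlier than under 3.3.5 for any T above 0.

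The direction of the difference depends on a definition that the protocol does not give.

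**Step 3. Which conflicts reach eligibility.** Exclusion 5 is applied at entry, so the conflict over acceptable methods can affect it. When a post-treatment period starts cannot.

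**The case against.** The strongest reply is that the female bullet can be read as a whole: a list, a specific instruction for oral contraception, then a general limit on everything before it. On that reading, a listed hormonal method needs a second method, and the advice in 3.2.1 and 3.2.2 points the same way. No sentence says that an implant or injectable suffices alone. This is a fair reading, but not the only one. The list is unconditional, and the sentence that says what to add names oral contraception only, so a site can reasonably conclude that other hormonal methods need nothing more.

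For men, the reply is that 3.2.1 and 3.2.2 defer to 3.3.5, whose own bullet for men requires barrier contraception. That weakens the conflict over method. The differences in force and in starting point remain.

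A reader might also infer three stronger things that the documents do not support:

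- *That men's protection lapses during dosing.* Section 3.3.5 binds men throughout dosing, 3.2.1 and 3.2.2 say that conception on treatment must be avoided, and Section 4.5.1.2 uses completion at patient level.
- *That patients would be wrongly enrolled and lost from analysis under Section 3.3.6.4.* This requires treating the 3.3.5 list as the definition behind exclusion 5, a link the protocol does not make.
- *That contraceptive failure is shown.* Section 1.1.2 reports CYP3A4 induction up to 55% of the rifampicin control at 0.1 µM and up to 97% at 1 µM. It also predicts relevant plasma concentrations below 1 µM and says the impact is still to be assessed. Pregnancy tests at screening, Visit 2 and every 8 weeks detect pregnancy but do not prevent it.

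**Conclusion.** The point holds as an inconsistency in operative text. Its core is the female rule: Section 3.3.5 allows opposite answers for a woman using only an implant or injectable, and exclusion 5 does not settle the matter. The inconsistent rule for men is secondary, and bears on counselling and post-treatment protection, not on entry.

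The number of patients affected is unknown. The protocol plans approximately 70 patients and gives no breakdown by sex, childbearing potential or contraceptive method. The conclusion rests on one outside assumption, that implants and injectables are hormonal. It does not depend on any view of which contraceptive rule is clinically right. The correction should be made because the concern is one the protocol itself raises and the change is to wording only.

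**What to change.** Reconcile Sections 3.2.1, 3.2.2, 3.3.4 and 3.3.5 so that:

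- one rule covers all hormonal methods (oral, implant, injectable), and the list, the added-barrier sentence and the last sentence of the bullet agree with it;
- one rule for men, with the same force and method, appears wherever it is stated;
- the start of the post-treatment period is defined once and used throughout;
- exclusion 5 refers to 3.3.5.

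The separate periods in 3.3.5 (4 weeks for women, 16 weeks for men) should stay distinct unless the sponsor changes them; nothing here shows either to be wrong. The sponsor's clinical team decides which rule and which starting point stand.

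The cost is a protocol amendment and a matching line in the consent form, with no added study procedures. Depending on the rule chosen, some patients may need to add or change a method.

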3.3.6 Discontinuation of patients from treatment or assessment

3.3.6.1 Criteria for discontinuation

Patients may be discontinued from study treatment and assessments at any time. Specific reasons for discontinuing a patient from this study are:

- Voluntary discontinuation by the patient who is at any time free to discontinue his/her participation in the study, without prejudice to further treatment

- Safety reasons as judged by the investigator and/or AstraZeneca
- Severe non-compliance to protocol as judged by the investigator and/or AstraZeneca
- Incorrect enrolment ie, the patient does not meet the required inclusion/exclusion criteria for the study (see Section 3.3.6.3)
- Patient lost to follow-up
- A female patient becoming pregnant
- Disease progression
- Deterioration in the patients condition which in the opinion of the Investigator warrants study medication discontinuation (to be recorded as an AE or under Investigator Discretion)
- Adverse Event

Specific reasons for discontinuing a patient from host genetic research are:

- Withdrawal of consent for host genetics research. A patient may withdraw from host or tumour genetic research at any time, independent of any decision concerning participation in other aspects of the main study described in this protocol. Voluntary discontinuation by the patient will not prejudice further treatment

3.3.6.2 Procedures for discontinuation

Patients who discontinue should always be asked about the reason(s) for their discontinuation and the presence of any adverse events. If possible, they should be seen and assessed by an investigator(s). Adverse events should be followed up.

Any serious adverse event (SAE) or non-serious AE considered related to study treatment by the investigator, which is ongoing at patient discontinuation from the study, or occurs within 30 days of the last study treatment must be followed up to resolution, unless the SAE is considered by the investigator to be unlikely to resolve.

AstraZeneca reserves the right to ask for further information/clarification on any AE that may be considered of interest.

3.3.6.3 Procedures for discontinuation from optional tumour biomarker aspects of the study (Part B only) (Not applicable)

No longer applicable.

